6.1.1 Serious Adverse Event Collection and Reporting

Sections 5.6.1 and 5.6.2 in the nivolumab IB represent the Reference Safety Information to determine expectedness of SAEs for expedited reporting. Following the subject's written consent to participate in the study, all SAEs, whether related or not related to study drug, must be collected, including those thought to be associated with protocol-specified procedures. All SAEs must be collected that occur during the screening period and within 100 days of discontinuation of dosing or within 30 days of the last visit for screen failures. For subjects randomized but never treated with any study drug, SAEs should be collected for 30 days from the date of randomization.

The investigator must report any SAE that occurs after these time periods and that is believed to be related to study drug or protocol-specified procedure.

An SAE report should be completed for any event where doubt exists regarding its seriousness.

If the investigator believes that an SAE is not related to study drug, but is potentially related to the conditions of the study (such as withdrawal of previous therapy or a complication of a study procedure), the relationship should be specified in the narrative section of the SAE Report Form.

SAEs, whether related or not related to study drug, and pregnancies must be reported to BMS (or designee) within 24 hours. SAEs must be recorded on the SAE Report Form; pregnancies on a Pregnancy Surveillance Form (electronic or paper forms). When using paper forms, the reports are to be transmitted via email or confirmed facsimile (fax) transmission to:

SAE Email Address: See Contact Information list.

SAE Facsimile Number: See Contact Information list.

For studies capturing SAEs/pregnancies through electronic data capture (EDC), electronic submission is the required method for reporting. The paper forms should be used and submitted

immediately, only in the event the electronic system is unavailable for transmission. When paper forms are used, the original paper forms are to remain on site.

SAE Telephone Contact (required for SAE and pregnancy reporting): See Contact Information list.

If only limited information is initially available, follow-up reports are required. (Note: Follow-up SAE reports should include the same investigator term[s] initially reported.)

If an ongoing SAE changes in its intensity or relationship to study drug or if new information becomes available, a follow-up SAE report should be sent within 24 hours to BMS (or designee) using the same procedure used for transmitting the initial SAE report.

All SAEs should be followed to resolution or stabilization.

A SUSAR (Suspected, Unexpected Serious Adverse Reaction) is a subset of SAEs and will be reported to the appropriate regulatory authorities and investigators following local and global guidelines and requirements.

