The planned sample size for Cohort B (ND, D) will be approximately 60 treated subjects, randomized in a 2:1 ratio in favor of the ND arm.

This is a Phase 1/2 study and the sample size in Cohort B is not powered for statistical hypothesis testing but is designed to evaluate both safety profile and clinical benefit of nivolumab with daratumumab.

If the true toxicities incidence rate in a cohort is 20% then with 20 patients in D cohort, there is 7% chance of observing 0 - 1 toxicities (false negative rate). If the true toxicities incidence rate in a cohort is 5% rather than 20%, then there is 26% chance that there will be at least 2 toxicities in 20 subjects (false positive rate). If the true toxicities incidence rate in a cohort is 20% then with 40 patients there is 3% chance of observing 0 - 3 toxicities (false negative rate). If the true toxicities incidence rate in a cohort is 5% rather than 20%, then there is 14% chance that there will be at least 4 toxicities in 40 subjects (false positive rate).

In 2 daratumumab monotherapy studies in relapsed/refractory MM patients, including a Phase 1/2 dose escalation study (GEN501)ⁱ in patients with at least 2 lines of prior therapy and a Phase 2 study (SIRIUS)ⁱⁱ in patients with at least 3 lines of prior therapy, the ORR were 36% and 29.2% respectively.

In two combination studies in relapsed/refractory MM patients with at least 2 lines of prior therapy, including a Phase 1b study of daratumumab in combination with pomalidomide and dexamethasoneⁱⁱⁱ and a Phase 1 dose-escalation study of pembrolizumab in combination with lenalidomide and dexamethasone,^{iv} the ORR were 60%.

Table 8.1-1 summarizes the 95% exact CI for the target ORRs ranging from 30% to 80% with sample size of 20 or 40 in a cohort. At observed ORR \geq 55% with 20 subjects, the lower bound of the 95% CI is 31.5%. At observed ORR \geq 77.5% with 40 subjects, the lower bound of the 95% CI is 61.5%.

Table 8.1-2 summarizes the 95% exact CI for the target MRD-target negativity rates ranging from 10% to 30% with sample size of 20 or 40 in a cohort. At observed MRD-target negativity rates \geq 30% with 20 subjects and observed MRD-target negativity rates \geq 20% with 40 subjects, the lower bound of the 95% CI are 11.9% and 9.1% respectively compares favorably to historical MRD-target negativity rate of 8% in recurrent pretreated relapsed or refractory MM.

Endpoints:

Safety:

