4 TREATMENTS

Study drugs include both Noninvestigational (NIMP) and Investigational Medicinal Products (IMP) and can consist of the following:

- All products, active or placebo, being tested or used as a comparator in a clinical trial
- Study required premedication, and
- Other drugs administered as part of the study that are critical to claims of efficacy (eg, backbone therapy, rescue medications)

Investigational Product

An investigational product, also known as investigational medicinal product in some regions, is defined as a pharmaceutical form of an active substance or placebo being tested or used as a reference in a clinical study, including products already with a marketing authorization but used or assembled (formulated or packaged) differently than the authorized form, or used for an unauthorized indication, or when used to gain further information about the authorized form.

The investigational product should be stored in a secure area according to local regulations. It is the responsibility of the investigator to ensure that investigational product is only dispensed to study subjects. The investigational product must be dispensed only from official study sites by authorized personnel according to local regulations.

In this protocol, investigational product(s) is/are: nivolumab and daratumumab.

Noninvestigational Product

Other medications used as support or escape medication for preventative, diagnostic, or therapeutic reasons, as components of the standard of care for a given diagnosis, may be considered as noninvestigational products.

Handling and Dispensing

The product storage manager should ensure that the study drug is stored in accordance with the environmental conditions (temperature, light, and humidity) as determined by the sponsor. If concerns regarding the quality or appearance of the study drug arise, do not dispense the study drug and contact the sponsor immediately.

Investigational product documentation must be maintained that includes all processes required to ensure drug is accurately administered. This includes documentation of drug storage, administration and, as applicable, storage temperatures, reconstitution, and use of required processes (eg, required diluents, administration sets).

For nivolumab and daratumumab, please refer to the current IB/pharmacy reference sheets for storage, handling and preparation instructions.

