4.1.1 Investigational Product

4.1.1.1 Nivolumab in the Nivolumab/Daratumumab Cohorts

Cohort A subjects: nivolumab will be administered at a dose of 240 mg as an intravenous infusion over 30 minutes every 2 weeks (Day 15 of Cycle 1, and Days 1 and 15 of each 28 day cycle during Cycles 2 through 6). Starting Cycle 7 and beyond, nivolumab will be administered at a dose of 480 mg as an intravenous infusion over 30 minutes every 4 weeks (Day 1 of each 28 day cycle).

Cohort B subjects: randomized to ND treatment (only): nivolumab will be administered at a dose of 240 mg as an intravenous infusion over 30 minutes on Day 15 of Cycle 1. Starting Cycle 2 and beyond, nivolumab will be administered at a dose of 480 mg as an intravenous infusion over 30 minutes every 4 weeks (Day 1 of each 28 day cycle).

Please refer to the nivolumab investigator brochure and/or pharmacy reference sheet/manual for guidelines on drug preparation and administration. Flush the intravenous line at the end of infusion.

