4.1.1.2 Daratumumab

Daratumumab injection for IV infusion is considered IMP for this study. Daratumumab vials must be stored in accordance with the package insert (USPI) /clinical supply labeling.⁷⁰

Daratumumab is an immunoglobulin G1 kappa (IgG1 κ) human monoclonal antibody against CD38 antigen, produced in a mammalian cell line (Chinese Hamster Ovary [CHO]) using recombinant DNA technology. The molecular weight of daratumumab is approximately 148 kDa.

Daratumumab is supplied as a colorless to pale yellow preservative-free solution for intravenous infusion in single-dose vials. Daratumumab must be diluted with 0.9% Sodium Chloride Injection, USP and to be administered as IV infusion according to the infusion rates specified in the (USPI)/pharmacy reference manual.⁷⁰

Daratumumab can cause severe infusion reactions, where about half of all patients in the studies to date experienced a reaction, most during the first infusion. Infusion reactions can also occur with subsequent infusions. Nearly all reactions occurred during infusion or within 4 hours of completing the daratumumab infusion.

Because of this high risk of infusion related reactions daratumumab infusions will be administered per the approved (USPI)/pharmacy reference manual⁷⁰ by a healthcare professional, with immediate access to emergency equipment and appropriate medical support to manage infusion reactions if they occur, and all subjects will receive pre-infusion and post-infusion medication per the approved (USPI)/pharmacy reference manual.⁷⁰

Before administration the drug product should be stored and prepared as per the instructions in current (USPI)/pharmacy reference manual.⁷⁰ The dose of daratumumab to be administered to a

subject will be calculated by multiplying the subject's weight (kg) by 16 mg/kg. The subject's predose weight on Day 1 of each cycle will be used to calculate the dose for each cycle. The dose does not need to be recalculated for weight changes that are < 10% from baseline. Each dose should be infused as per instructions in the current daratumumab (USPI)/pharmacy reference manual.⁷⁰

For the administration of the first 16 mg/kg dose of daratumumab, in addition to previously approved single first infusion on Cycle 1 Day 1, a split-dosing regimen (ie, splitting the first dose over two consecutive days at 8 mg/kg on Cycle 1 Days 1 and 2) was recently approved in EU, US, and Canada. Investigators are allowed to opt for the split-dosing regimen.

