10 GLOSSARY OF TERMS

Term	Definition
Adverse Reaction	An adverse event that is considered by either the investigator or BMS as related to the investigational product
Unexpected Adverse Reaction	An adverse reaction, the nature or severity of which is not consistent with the applicable product information (eg, Investigator Brochure for an unapproved investigational product)

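### Section 6.1.1 names only the nivolumab brochure as the reference for SAE expectedness, although daratumumab is also investigational and the D arm never receives nivolumab

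*Protocol*

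**What the plan says.** Protocol Section 6.1.1 sets the reference in one sentence: "Sections 5.6.1 and 5.6.2 in the nivolumab IB represent the Reference Safety Information to determine expectedness of SAEs for expedited reporting". The sentence is not limited to events attributed to nivolumab or to arms that receive it. The same section then says that SUSARs go to regulators and investigators under the guidelines that apply, without naming a further reference document.

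Section 4 says "In this protocol, investigational product(s) is/are: nivolumab and daratumumab", and Section 4.1.1.2 repeats the point: "Daratumumab injection for IV infusion is considered IMP for this study".

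In Cohort B, nivolumab goes to one arm only. Section 4.1.1.1 reads "Cohort B subjects: randomized to ND treatment (only): nivolumab will be administered at a dose of 240 mg", with the first dose on Day 15 of Cycle 1. Daratumumab starts on Day 1 (Section 4.1.4.2). The synopsis plans "approximately 60 treated subjects, randomized in a 2:1 ratio in favor of the ND arm".

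The glossary (Section 10) defines an unexpected adverse reaction as "An adverse reaction, the nature or severity of which is not consistent with the applicable product information". The daratumumab brochure, package insert and US label are cited for storage, preparation, infusion management and blood-typing interference (Sections 4, 4.1.1.2 and 4.1.3). The readable text never cites them for expectedness.

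**The concern.** Expectedness decides whether a suspected serious reaction is a SUSAR, and so whether regulators and investigators hear of it on the expedited route. That judgement is meaningful only against the known profile of the product under suspicion. Here one product's brochure is named for a trial with two investigational products, one of which is given on its own to a whole randomized arm.

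Tolerability is the primary objective, Section 7 provides for no data monitoring committee, and the toxicity stopping rules in Section 3.1.1.1 apply to the ND arm only. A correct expedited-reporting rule therefore matters for the D arm. What is at stake is the classification and onward reporting of suspected daratumumab reactions. The trial's endpoints are not affected: the primary endpoints in Section 8.3.1.1 count drug-related grade 3-4 AEs and SAEs and laboratory abnormalities, and none of them uses expectedness.

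**Working it through.** The plan gives no figure to reproduce. The check is the size of the exposed group, followed by the logic of the rule.

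**Who is on daratumumab without nivolumab**

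Inputs: about 60 subjects, 2:1 in favor of ND (synopsis); first daratumumab on Cycle 1 Day 1 (Section 4.1.4.2); first nivolumab on Cycle 1 Day 15 (Section 4.1.1.1).

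- D arm: 60 × 1/3 = 20 subjects, or 20/60 = 33% of Cohort B, with no nivolumab at any time.
- ND arm: 60 × 2/3 = 40 subjects. Days before the first nivolumab dose, on schedule: 15 − 1 = 14, on daratumumab alone.

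Every Cohort B subject therefore has some time on daratumumab before or without nivolumab. These are counts of subjects and days, not of misclassified events.

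**What the sentence in 6.1.1 does to an event**

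Take an SAE suspected to be due to daratumumab in a subject who has not received nivolumab. Compare the literal rule with a rule that uses the suspected product's own reference.

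| Listed for nivolumab | Listed for daratumumab | Literal 6.1.1 | Product-specific rule | Result |
|---|---|---|---|---|
| Yes | Yes | Expected | Expected | Same |
| No | No | Unexpected | Unexpected | Same |
| Yes | No | Expected | Unexpected | SUSAR not expedited |
| No | Yes | Unexpected | Expected | Over-reported |

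Two of the four combinations agree and two do not, one in each direction.

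**Which rows the documents can illustrate**

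- *Infusion reactions.* Section 4.1.1.2 says "Daratumumab can cause severe infusion reactions, where about half of all patients in the studies to date experienced a reaction", mostly at the first infusion, which precedes nivolumab. It presents them as known for daratumumab. If the daratumumab reference lists them, they fall in the first or fourth row: agreement or over-reporting. They do not illustrate a missed SUSAR.
- *Immune-type toxicities.* Pneumonitis, uveitis and myocarditis appear in the nivolumab discontinuation criteria (Section 4.1.5.1) and not in the daratumumab criteria (Section 4.1.5.2). If the two references differ in the same way, such an event suspected on daratumumab alone would fall in the third row. This is an assumption, because neither brochure is in the documents.

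**Side by side with the glossary**

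For a D-arm subject, the product information that applies to a suspected reaction cannot be that of a drug never given. Taken literally, Section 6.1.1 and Section 10 give different tests for the same event.

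**The case against.** The strongest reply is that the two sections can be read together. Section 6.1.1 names nivolumab's reference, does not expressly exclude others, and leaves daratumumab events to the glossary and to the reporting guidelines. The protocol plainly knows of a daratumumab brochure and label. This reply stands in part: it makes the matter an internal inconsistency to reconcile. It does not remove it, because the specific sentence covers SAEs without restriction and no general wording names a daratumumab reference or overrides it.

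A reader might infer more than the documents support:

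- *That daratumumab reactions cannot be classified correctly.* The generic wording leaves room for a product-specific practice, so this does not follow.
- *That SUSARs have already been missed.* The documents do not describe how the sponsor has judged expectedness in these cohorts. Nothing shows that any past event was misclassified.
- *That the error is only under-reporting.* It runs both ways, and the best-documented daratumumab reaction points to agreement or over-reporting.
- *That safety oversight depends mainly on this rule.* All SAEs, related or not, reach the sponsor within 24 hours (Section 6.1.1). AE data are monitored continuously (Section 3.1). An interim safety and efficacy analysis covers both Cohort B arms (Section 8.5.1). None of these uses expectedness.

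**Conclusion.** The concern holds as a wrong rule as written. Applied literally, Section 6.1.1 judges suspected daratumumab reactions against nivolumab's profile, including in the roughly 20 of 60 Cohort B subjects who never receive nivolumab and in the roughly 40 ND subjects during their first 14 days. It conflicts with the glossary and allows misclassification in both directions.

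The exposure figures assume the planned 60 subjects, the 2:1 split and on-schedule dosing. The number of events affected cannot be determined without the two brochures. The conclusion concerns expectedness and expedited onward reporting only; SAE collection and the trial's analyses are untouched. Because the change is small and specific, it should go into the next protocol revision.

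**What to change.** In Section 6.1.1:

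- Name a Reference Safety Information document and section for daratumumab alongside the nivolumab one. Choose one document, since a choice between brochure and label would leave the reference undetermined.
- State that expectedness is judged separately for each suspected product that the subject has received.
- State that an event unexpected for any suspected product is a SUSAR. This also settles events attributed to the combination.
- State that the nivolumab reference does not apply to D-arm subjects or to events before the first nivolumab dose.

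The sponsor should also confirm which reference was used for related SAEs in the nivolumab/daratumumab cohorts so far, and reclassify them only if the nivolumab brochure alone was used.

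The cost is a wording change, that confirmation, and possibly a few more expedited reports. No new data, visits or subjects are needed.

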6.2 Nonserious Adverse Events

A *nonserious adverse event* is an AE not classified as serious.

6.2.1 Nonserious Adverse Event Collection and Reporting

The collection of nonserious AE information should begin at initiation of study drug. Nonserious AE information should also be collected from the start of a placebo lead-in period or other observational period intended to establish a baseline status for the subjects. All non-serious AEs (not only those deemed to be treatment-related) should be collected continuously during the treatment period and for a minimum of 100 days following the last dose of study drug treatment.

Nonserious AEs should be followed to resolution or stabilization, or reported as SAEs if they become serious (see [Section 6.1.1](#)). Follow-up is also required for nonserious AEs that cause interruption or discontinuation of study drug and for those present at the end of study treatment as appropriate. All identified nonserious AEs must be recorded and described on the nonserious AE page of the CRF (paper or electronic).

Completion of supplemental CRFs may be requested for AEs and/or laboratory abnormalities that are reported/identified during the course of the study.

6.3 Laboratory Test Result Abnormalities

The following laboratory test result abnormalities should be captured on the nonserious AE CRF page or SAE Report Form (paper or electronic) as appropriate:

- Any laboratory test result that is clinically significant or meets the definition of an SAE
- Any laboratory test result abnormality that required the subject to have study drug discontinued or interrupted
- Any laboratory test result abnormality that required the subject to receive specific corrective therapy.

It is expected that wherever possible, the clinical rather than laboratory term would be used by the reporting investigator (eg, anemia versus low hemoglobin value).

6.4 Pregnancy

If, following initiation of the investigational product, it is discovered that a study subject is pregnant or may have been pregnant at the time of investigational product exposure, including during at least time to washout plus one ovulatory cycle (30 days) for a total of 23 weeks, or plus one spermatogenesis cycle (90 days) for a total of 31 weeks after product administration, the investigator must immediately notify the BMS Medical Monitor/designee of this event and complete and forward a Pregnancy Surveillance Form to BMS Designee within 24 hours of awareness of the event and in accordance with SAE reporting procedures.

In most cases, the study drug will be permanently discontinued in an appropriate manner (eg, dose tapering if necessary for subject safety). Please call the BMS Medical Monitor within 24 hours of awareness of the pregnancy.

Follow-up information regarding the course of the pregnancy, including perinatal and neonatal outcome and, where applicable, offspring information, must be reported on the Pregnancy Surveillance Form.

Any pregnancy that occurs in a female partner of a male study participant should be reported to BMS. Information on this pregnancy will be collected on the Pregnancy Surveillance Form.

6.5 Overdose

An overdose is defined as accidental or intentional administration of any dose of product that is considered both excessive and medically important. All occurrences of overdose must be reported as SAEs (see [Section 6.1.1](#) for reporting details).

6.6 Potential Drug Induced Liver Injury (DILI)

Wherever possible, timely confirmation of initial liver-related laboratory abnormalities should occur prior to the reporting of a potential DILI event. All occurrences of potential DILIs, meeting the defined criteria, must be reported as SAEs (see [Section 6.1.1](#) for reporting details).

Potential drug induced liver injury is defined as

1) AT (ALT or AST) elevation > 3 times upper limit of normal (ULN)

AND

2) Total bilirubin > 2 times ULN, without initial findings of cholestasis (elevated serum alkaline phosphatase),

AND

3) No other immediately apparent possible causes of AT elevation and hyperbilirubinemia, including, but not limited to, viral hepatitis, pre-existing chronic or acute liver disease, or the administration of other drug(s) known to be hepatotoxic.

